#### X. REPORTING REQUIREMENTS

All adverse and serious adverse events will be recorded and reported according to the Department of Leukemia guidelines (appendix C)

## **XI. STATISTICAL CONSIDERATIONS**

This is a Phase II study of clofarabine, idarubicin, cytarabine, vincristine, and corticosteroids for patients with newly diagnosed or relapsed/refractory mixed phenotype acute leukemia

The primary objective is to evaluate the efficacy, with primary endpoint of response (CR or CRi) during a 2 month window. The two groups of patients will be evaluated separately; however accrual to both groups will be concurrent.

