There is no standard therapy for the group of patients diagnosed with MPAL, and the situation presents a clinical challenge that has not been well studied. Most experience to date comes from the pediatric literature and from older case series. Killick and colleagues identified 25 cases of "biphenotypic" leukemia of 693 cases (3.6%) of acute leukemia over an 8 year period [3]. This cohort included pediatric patients as young as 3 years of age, and adults up to age 46. A wide variety of induction regimens were used, including conventional ALL induction, conventional AML induction, as well regimens that used agents typically used to treat both lineages. Median overall survival (OS) for the 20 de novo patients was 27.3 weeks, which is very poor considering a median age of 25.5 years. Importantly, several patients also had the Philadelphia chromosome, and treatment was before the era of tyrosine kinase inhibitors.

Recently, a group from Saudi Arabia described the clinical characteristics and outcome of 24 pediatric patients diagnosed with MPAL [4]. All patients were treated uniformly with a modified St. Jude Total Therapy-B HR regimen, which that group uses to treat high risk ALL [5]. This regimen involves at least six drugs with activity against lymphoid and myeloid leukemias. All patients were also considered for allogeneic stem cell transplantation (alloSCT) in first complete remission (CR). For patients not undergoing alloSCT, maintenance therapy was continued for 2.5 years. With a median follow up of four years, the survival was 75.7%, which is excellent, but must be interpreted keeping

in mind that the median age was 8.7 years. AlloSCT did not improve the outcome in this small study.

The St. Jude's Children's Research Hospital has recently published their own experience treating pediatric patients with mixed lineage acute leukemias [6]. Thirty-five patients were treated, and the median age was 10. Overall, 23 patients received AML induction (daunorubicin, cytarabine, etoposide), and 12 received standard ALL induction (vincristine, daunorubicin, L-asparaginase, prednisone). Patients receiving AML or ALL induction regimens up front achieved CR rates of 52% and 83%, respectively. Eighty percent of the patients not achieving CR after AML induction subsequently went into CR after ALL induction. The 5-year OS for patients with B/Myeloid or T/Myeloid was 47.8%.

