The frontline strategy for the management of adult ALL is similar to pediatrics, and involves induction chemotherapy, multiple rounds of consolidation, a prolonged maintenance phase, as well as central nervous system (CNS) prophylaxis. Most protocols call for approximately 3 years of therapy in total. There are several accepted regimens employed in the United States, and most involve the same key agents which include vincristine, anthracycline (e.g., doxorubicin or daunorubicin), corticosteroids (e.g., prednisone or dexamethasone), with or without some form of L-asparaginase [15-17]. One such regimen is the hyperCVAD, which employs the combination of hyperfractionated cyclophosphamide, vincristine, doxorubicin, and dexamethasone alternating with high dose methotrexate and cytarabine [18, 19]. Cycles are repeated approximately monthly for 8 cycles, a point at which patients move to the maintenance portion of the regimen with daily mercaptopurine, monthly vincristine, weekly methotrexate, and monthly pulses of prednisone (POMP). Long term outcomes have been published previously, with five year overall survival (OS) of 38%. Survival was influenced by several prognostic factors that were assessed using multivariable analysis. This is comparable to a number of other regimens that are used depending on center preference.

At the M.D. Anderson Cancer Center (MDACC), MPAL has traditionally been treated with AML induction regimens. It may be optimal to also administer agents that are predominantly used against ALL. Therefore, we are proposing to use a hybrid regimen, with components of both AML and ALL therapy, to treat patients diagnosed with MPAL at MDACC. The backbone of the regimen will be our standard induction for AML, clofarabine, idarubicin, and cytarabine administered at attenuated doses. Importantly, all three of these drugs also have activity against ALL. In addition, we will add vincristine and corticosteroids to the regimen for enhanced lymphoid activity. These are ideal candidates for addition to the regimen for a number of reasons. First, the toxicity profiles do not overlap, allowing us to safely give all five agents during the same course of therapy. Second, corticosteroids are routinely used as a premedication to prevent toxicity induced by moderate to high doses of cytarabine, albeit at lower doses.

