Patients, who have not achieved a complete remission (CR)/complete remission without platelet (CRi) recovery following one induction course can receive a second induction course to optimize response if possible. A second induction course at the same dose as the previous course or in a dose-reduced fashion should not be given until at least 28 days of course 1. If the bone marrow aspirate and/or biopsy(s) performed after the reinduction cycle reveals a remission marrow (CR/CRi), then the patient may proceed with consolidation at the discretion of the treating investigator. In addition, any clinically significant drug-related, non-hematologic toxicity experienced by a patient should return to ≤ grade 2 or the baseline grade before the patient continues treatment. Should the patient not have achieved a remission, including CR and CRi after the re-induction course, he/she will be taken off study for failure to respond, unless the patient has

achieved clinical benefit or partial remission, at which time further therapy on protocol may be permitted with approval from the PI.

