## **During induction therapy**

- 1. CBC, differential, and platelet count every 3-7 days (the differential may be omitted when the WBC is < 500.). Creatinine, bilirubin, ALT (SGPT) and/or AST (SGOT) once weekly.
- 2. Physical exam including vital signs (temperature, heart rate, respiratory rate, blood pressure) and performance status. Prior to each treatment course
- 3. Bone marrow aspirate and/or biopsy on day 28 +/- 7 days to confirm complete remission. Cytogenetics as clinically indicated.

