## 1.1 Response

The historical data suggested that the response rate in the standard treatment for the study patient is about 50%, it is anticipated that with the study treatment the response rate will increase to 70%.

Response will be monitored closely in all patients using the method of Thall et al (20). The interim monitoring will begin after 10 patients have been enrolled to the study, and then by a cohort of 5 patients. Denote the probabilities of response for the standard treatment and this experimental study by  $P_S$  and  $P_E$ , respectively. We assume  $P_S \sim$  beta(50, 50) to reflect the historical response rate and  $P_E \sim$  beta (1, 1), which have the

same response rate but a bigger various. We will stop the trial if at any point Pr ( $P_E > P_S + 0.2 \mid data$ ) < 0.01. That is, we will stop the trial if, at any time during the study, we determine that there is less than 1% chance that the response rate in the study is 20% more than that of the standard treatment. Stopping boundaries corresponding to this stopping rule and operating characteristics are listed in table 1a and 1b respectively. For example, if 3 or fewer patients have response in the first 10 patients, the trial will be stopped.

If the study is not stopped early and all 40 patients have been enrolled to the study and evaluated, and assuming that 28 out of the 40 patients have response to the treatment, then the 95% credible interval for the response rate will be (0.54, 0.82).

Table 1a: The trial will be monitored according to the following stopping boundaries for CR/CRi.

Number of Patients Evaluated	Recommend Stopping if Response Observed in n or less patients
10	3
15	5
20	8
25	11
30	13
35	16

Table 1b: Operating characteristics for response monitoring

True CR Probability	Probability of Early Stop	Achieved Sample Size Percentile (10 25 50 75 90)
0.3	0.99	10 10 10 15 20
0.4	0.861	10 10 20 25 40
0.5	0.487	10 20 40 40 40
0.6	0.137	25 40 40 40 40
0.7	0.018	40 40 40 40 40
0.8	0.0009	40 40 40 40
0.9	<0.0001	40 40 40 40 40

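### Does the 2-month response window credit a second induction course that the 50% historical benchmark leaves out?

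*Combined protocol and SAP*

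**What the plan says.** Section XI gives the "primary endpoint of response (CR or CRi) during a 2 month window". It does not say when the window opens, how many days it lasts, or how a response after a second course is handled.

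Under V.2 (Induction), a patient without CR or CRi after one course "can receive a second induction course to optimize response if possible"; that course "should not be given until at least 28 days of course 1". Section VI schedules a "Bone marrow aspirate and/or biopsy on day 28 +/- 7 days to confirm complete remission".

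Section 1.1 supplies the benchmark: "The historical data suggested that the response rate in the standard treatment for the study patient is about 50" percent, with 70% anticipated on study treatment. It cites no source for the 50%. The figure is carried into a Beta(50,50) prior for the standard rate. The trial stops for futility if the posterior probability that the study rate exceeds the standard rate by 0.20 is below 0.01.

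The Rationale (section II) describes a pediatric series: "Patients receiving AML or ALL induction regimens up front achieved CR rates of 52% and 83%, respectively". It adds: "Eighty percent of the patients not achieving CR after AML induction subsequently went into CR after ALL induction". It also says that at this center "MPAL has traditionally been treated with AML induction regimens".

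**The concern.** A single-arm trial depends on its historical rate being measured in the same way as its endpoint. Here the endpoint can take in two courses and counts CRi, while the benchmark's basis is not stated.

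The only CR rate near 50% in the protocol is the pediatric 52%. It is a rate after up-front AML induction, and AML induction is what this center has traditionally used. In that series the rate rose to about 87-90% once the failures were re-induced. If the 50% came from there, two courses would be set against one. A regimen no better than standard on its first course could then reach 70%, and the futility rule would rarely stop it. The Beta(50,50) prior has a 95% range of 0.40-0.60, so it could not absorb a much higher matched rate.

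**Working it through.** **1. The plan's own figures reproduce.** Inputs from section 1.1: standard rate ~ Beta(50,50), study rate ~ Beta(1,1), margin 0.20, cutoff 0.01, looks at 10 to 35 patients in steps of 5, maximum 40.

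- At 10 patients, the probability of exceeding the standard by 0.20 is 0.0068 with 3 responses (stop) and 0.0288 with 4 (continue).
- Repeating this at each look gives boundaries 3, 5, 8, 11, 13, 16, exactly as in Table 1a.
- Exact early-stop probabilities at true rates 0.5, 0.6, 0.7, 0.8 are 0.488, 0.139, 0.018, 0.001. Table 1b has 0.487, 0.137, 0.018, 0.0009.
- For 28/40 the posterior is Beta(29,13), with a 95% interval of 0.545-0.819. The plan gives 0.54-0.82.

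**2. How much a mismatch could matter.** Suppose the first-course rate is 0.50 and a share c of first-course failures responds to course 2 inside the window. The 2-month rate is 0.50 + 0.50 × c. The protocol gives no value for c, so these are assumed values.

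| c | 2-month rate | P(early stop) | P(at least 28/40) |
|---|---|---|---|
| 0 | 0.50 | 0.488 | 0.008 |
| 0.2 | 0.60 | 0.139 | 0.129 |
| 0.4 | 0.70 | 0.018 | 0.577 |
| 0.5 | 0.75 | 0.005 | 0.821 |

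A mismatch would therefore be material, if there is one.

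**3. Where 87-90% comes from.** Of 23 AML-induced children, 52% is 12 in CR and 11 not. From the percentages, 0.52 + 0.48 × 0.80 = 0.904. If 8 of 10 re-treated children responded, (12 + 8)/23 = 0.870. The gap from 52% is 35 to 38 points. It measures a switch from AML to ALL induction in children with a median age of 10. In this trial the patients are adults, and course 2 repeats or dose-reduces a regimen that already combines AML and ALL agents.

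**4. Which second-course responses fit the window.** Assume that the day 28 ± 7 marrow also applies to course 2 and that two months is about 61 days. The nominal marrow then falls on start day + 27.

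- Start on day 29: 29 + 27 = day 56, inside.
- Start on day 34: 34 + 27 = day 61, at the edge.
- Start on day 36, just after the latest scheduled first marrow (day 35): 36 + 27 = day 63, outside.

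So a second-course response can count, but does so reliably only after a prompt restart.

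**5. What the remedies would do.**

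- Scoring response at the first-course day 28 ± 7 marrow would fail a one-course responder whose neutrophils recover after day 35, because both CR and CRi require neutrophils of at least 1.0 × 10⁹/L (section IX). The protocol expects slow recovery in some patients: V.4 provides for cytopenia lasting beyond 42 days.
- Centering the prior on 0.87 makes the target 0.87 + 0.20 = 1.07, which is above 1. With the same prior weight of 100, the rule would stop even at 10 responses in 10.

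**The case for a change.** The strongest case is that a reader cannot verify the match. Section 1.1 names no source, does not separate CR from CR/CRi and does not mention re-induction. There is no concurrent control to expose an error. Even a modest c of 0.2 cuts the early-stop probability from 0.49 to 0.14. At 28/40, the probability that the study rate exceeds the Beta(50,50) standard is 0.98, so a result built on two courses could be read as an improvement.

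The missing definition stands, and so does the sensitivity to c. The step from there to a biased comparison does not. It needs the 50% to be a first-course rate, and the only support is that 52% is numerically close. The 0.98 is also not a test in the plan: section 1.1 has a futility rule and no success criterion, and the Analysis Plan reports a posterior rate with a 95% credible interval. If the benchmark were low, the futility rule would be lenient, but the separate mortality and toxicity rules (sections 1.2 and 1.3) would operate as before.

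**Conclusion.** The concern does not call for a change. Sections XI and 1.1 leave out the window's start and length, the handling of course 2, and the source of the 50%. Section 1.1 nevertheless applies one term, response rate, to both the 50% and the 70%, directly under an endpoint defined as CR or CRi in 2 months. The plain reading is that all three are on the same basis. An analyst would naturally count the window from the start of treatment, accept any CR or CRi inside it, and show response by course with CR and CRi apart. None of that alters the design.

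The 35 to 38 point gap is not an estimate of bias in this trial. The scenarios that take a 50% first-course rate to 60-75% rest on assumed rescue rates. A two-month window is also a reasonable choice in its own right, since it allows for slow count recovery after a single course. The two substantive remedies would make matters worse: one misclassifies late-recovering responders, and the other gives an unusable margin.

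This conclusion assumes that the 50% was taken on the endpoint's own definition. The protocol implies that but does not state it. If the sponsor's source proved to be a first-course CR rate, the table above shows how far the reading of a 70% result would weaken.

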## Part I: Newly diagnosed patients

A maximum of 40 newly diagnosed will be enrolled. The toxicity, 4-week mortality rate, and efficacy (response) will be monitored during the study, and all the data will be used to update the prior distributions for toxicity and efficacy parameters. The study will be stopped for toxicity, 4-week mortality and futility based on the following stopping rules.

## 1.1 Response

The historical data suggested that the response rate in the standard treatment for the study patient is about 50%, it is anticipated that with the study treatment the response rate will increase to 70%.

Response will be monitored closely in all patients using the method of Thall et al (20). The interim monitoring will begin after 10 patients have been enrolled to the study, and then by a cohort of 5 patients. Denote the probabilities of response for the standard treatment and this experimental study by  $P_S$  and  $P_E$ , respectively. We assume  $P_S \sim$  beta(50, 50) to reflect the historical response rate and  $P_E \sim$  beta (1, 1), which have the

same response rate but a bigger various. We will stop the trial if at any point Pr ( $P_E > P_S + 0.2 \mid data$ ) < 0.01. That is, we will stop the trial if, at any time during the study, we determine that there is less than 1% chance that the response rate in the study is 20% more than that of the standard treatment. Stopping boundaries corresponding to this stopping rule and operating characteristics are listed in table 1a and 1b respectively. For example, if 3 or fewer patients have response in the first 10 patients, the trial will be stopped.

If the study is not stopped early and all 40 patients have been enrolled to the study and evaluated, and assuming that 28 out of the 40 patients have response to the treatment, then the 95% credible interval for the response rate will be (0.54, 0.82).

Table 1a: The trial will be monitored according to the following stopping boundaries for CR/CRi.

Number of Patients Evaluated	Recommend Stopping if Response Observed in n or less patients
10	3
15	5
20	8
25	11
30	13
35	16

Table 1b: Operating characteristics for response monitoring

True CR Probability	Probability of Early Stop	Achieved Sample Size Percentile (10 25 50 75 90)
0.3	0.99	10 10 10 15 20
0.4	0.861	10 10 20 25 40
0.5	0.487	10 20 40 40 40
0.6	0.137	25 40 40 40 40
0.7	0.018	40 40 40 40 40
0.8	0.0009	40 40 40 40
0.9	<0.0001	40 40 40 40 40

## 1.2 4-week mortality

Mortality in the first 4 weeks will be monitored closely in patients using the method of Thall et al (1995). Denote the probability of death within 4 weeks by DE. We assume DE  $\sim$  beta (0.2, 1.8). We will stop the trial if at any point Pr(DE > 0.1 | data) >0.90. That is, we will stop the trial if, at any time during the study, we determine that there is more than 95% chance that the mortality rate is more than 10%. The trial will be stopped if (the number of death in the 1st 4 weeks observed) / (among the number of patients)  $\geq$  3/10, 4/12, 5/19, 6/26 and 7/33. The operating characteristics are listed in table 2.

Table 2: The operating characteristics for mortality monitoring are summarized in the following table

True probability of death	Probability of early stop	Sample size percentiles (10, 25, 50, 75, 90)
0.01	<0.0001	40 40 40 40 40

0.05	0.027	40 40 40 40 40
0.1	0.191	16 40 40 40 40
0.15	0.509	10 15 39 40 40
0.2	0.782	10 10 17 37 40
0.25	0.924	10 10 11 22 36

# 1.3 Toxicity

Toxicity will be monitored closely in all patients using the method of Thall et al (1995). Denote the probability of toxicity by  $\theta_E$ , where toxicity is defined as any Grade 3 or greater clinically significant non-hematological toxicities related to the treatment. We assume  $\theta_E \sim$  beta (0.6, 1.4). We will stop the trial if we  $\Pr(\theta_E > 0.30 \mid data) > 0.92$ . That is, we will stop the trial if, at any time during the study, we determine that there is more than 95% chance that the toxicity rate is more than 30%. Stopping boundaries corresponding to this stopping rule and operating characteristics are listed in table 3a and 3b respectively.

Table 3a: The trial will be stopped according to the following boundaries for toxicities

Number of Patients Evaluated	Recommend Stopping if Toxicity Observed in n or more patients
10	6
15	8

20	10
25	12
30	14
35	16

Table 3b: The operating characteristics for toxicity monitoring are summarized in the following table

True toxicity probability	Probability of early stop	Sample size percentiles (10, 25, 50, 75, 90)
0.1	0.0001	40 40 40 40 40
0.2	0.011	40 40 40 40 40
0.3	0.112	30 40 40 40 40
0.4	0.446	10 15 40 40 40
0.5	0.833	10 10 15 30 40
0.6	0.981	10 10 10 15 25

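### The Part I toxicity stopping rule gives a 0.92 cut-off in its formula, but its explanation says 95% and Tables 3a and 3b fit 0.95, so formula and table disagree at 13/30 and 15/35

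*Combined protocol and SAP*

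**What the plan says.** Section 1.3 (Part I, newly diagnosed patients) gives the toxicity probability θ a beta(0.6, 1.4) prior and sets the stopping condition on the posterior probability that θ exceeds 0.30. The cut-off then appears in three forms:

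- **Formula:** "0.30 \mid data) > 0.92".
- **Explanation, in the next sentence:** stop if "we determine that there is more than 95% chance that the toxicity rate is more than 30" per cent.
- **Tables:** "Stopping boundaries corresponding to this stopping rule and operating characteristics are listed in table 3a and 3b respectively". Table 3a is introduced with "The trial will be stopped according to the following boundaries for toxicities" and stops at 6/10, 8/15, 10/20, 12/25, 14/30 and 16/35. Table 3b prints early-stop probabilities of 0.0001, 0.011, 0.112, 0.446, 0.833 and 0.981 at true toxicity rates of 0.1 to 0.6.

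The Part I maximum is 40 patients ("A maximum of 40 newly diagnosed will be enrolled").

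**The concern.** The explanation is offered as a restatement of the formula, and the tables as its consequence, so all three should carry the same threshold. They do not. The difference would be harmless if 0.92 and 0.95 gave the same integer boundaries at every look, so the question is whether any decision changes and which version the printed operating characteristics describe.

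The stake is a safety stop for the whole newly diagnosed cohort. A monitor working from the formula and one working from Table 3a could reach opposite decisions on the same data. Anyone approving the plan on the formula would believe the rule is stricter than the one tabulated.

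**Working it through.** **Inputs.** Prior beta(0.6, 1.4), toxicity limit 0.30, cut-offs 0.92 and 0.95, and the printed boundaries and operating characteristics all come from section 1.3. Maximum N = 40 is from the opening of Part I. Looks are at 10, 15, 20, 25, 30 and 35 patients, which are the rows of Table 3a. Section 1.1 states this schedule in words, for response ("The interim monitoring will begin after 10 patients have been enrolled to the study, and then by a cohort of 5 patients").

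**Posterior.** With x toxicities in n patients, θ given the data is Beta(0.6 + x, 1.4 + n − x). The boundary at n is the smallest x with Pr(θ > 0.30 | x, n) above the cut-off.

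| n | Table 3a boundary | Posterior at the boundary | Posterior one below | Boundary at 0.95 | Boundary at 0.92 |
|---|---|---|---|---|---|
| 10 | 6 | 0.962 | 0.880 (5/10) | 6 | 6 |
| 15 | 8 | 0.960 | 0.893 (7/15) | 8 | 8 |
| 20 | 10 | 0.961 | 0.906 (9/20) | 10 | 10 |
| 25 | 12 | 0.963 | 0.918 (11/25) | 12 | 12 |
| 30 | 14 | 0.967 | **0.929 (13/30)** | 14 | **13** |
| 35 | 16 | 0.970 | **0.938 (15/35)** | 16 | **15** |

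Example at n = 30, x = 13: the posterior is Beta(13.6, 18.4), and its tail above 0.30 is 0.9286. That is above 0.92 and below 0.95.

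Table 3a is reproduced by any cut-off from 0.9379 (the posterior at 15/35) up to just under 0.9597 (the posterior at 8/15). The value 0.95 lies in that range and 0.92 does not.

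**Operating characteristics.** The number of toxicities was carried forward patient by patient with binomial probabilities. At each look, all probability at or above the boundary was removed as stopped. Early stopping is the sum removed at the six looks.

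| True rate | Table 3b | Boundaries at 0.95 | Boundaries at 0.92 | 0.92 minus Table 3b |
|---|---|---|---|---|
| 0.1 | 0.0001 | 0.0002 | 0.0002 | 0.0001 |
| 0.2 | 0.011 | 0.010 | 0.012 | 0.001 |
| 0.3 | 0.112 | 0.111 | 0.142 | 0.030 |
| 0.4 | 0.446 | 0.445 | 0.531 | 0.085 |
| 0.5 | 0.833 | 0.830 | 0.887 | 0.054 |
| 0.6 | 0.981 | 0.982 | 0.991 | 0.010 |

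At 0.95 every row agrees with Table 3b to within 0.003, and all printed sample-size percentiles are reproduced. At 0.92 the gap reaches 0.085, and the median sample size at a true rate of 0.4 becomes 35 where the table prints 40.

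**Other readings that might rescue 0.92.**

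- A uniform beta(1, 1) prior with 0.92 gives boundaries 5, 7, 9, 11, 13, 15, which is not Table 3a.
- Looking after every patient from the tenth on with 0.92 gives early stopping of 0.206 at a true rate of 0.3, against 0.112 printed.

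**The case against.** The strongest reply is that Table 3a is the working instruction, that it agrees with Table 3b, and that a monitor who uses the table has a clear rule with correctly stated properties. The two versions coincide at four of six looks and differ by one patient at the other two. All of this is true. It limits the practical harm, but the written rule still contradicts its own table.

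A second objection is that the 95% wording is weak evidence of intent. Section 1.2 (4-week mortality) also pairs a 95% explanation with a different formula cut-off, 0.90, and there the formula is what fits. With its beta(0.2, 1.8) prior, the printed boundaries 3/10, 4/12, 5/19, 6/26 and 7/33 follow from 0.90, while 0.95 would require 4/10. Moreover, the toxicity tables fit a range of cut-offs and do not single out 0.95. This stands, and it is why the intended value is for the sponsor to confirm. It also shows that no general convention settles the matter: the boundaries follow the formula in 1.2 and the explanation in 1.3.

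A third point is that the five-patient look schedule is stated in words only for response, while the toxicity text speaks of stopping at any time. The rows of Table 3a and the match with Table 3b support the five-patient schedule. If toxicity were checked after every patient, the two cut-offs would part earlier, first at n = 11 (6 against 7 toxicities), so the disagreement would be wider.

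**Conclusion.** The concern holds, and the rule must be corrected. The formula's 0.92 conflicts with the explanation and with both tables. On the schedule of Table 3a, the conflict changes the decision at exactly two looks: 13/30 and 15/35, where the formula stops and the table continues.

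The largest effect is at a true toxicity rate of 0.4. There the formula stops with probability 0.531 and the tabulated rule with 0.445, a difference of 8.6 percentage points (8.5 against the printed 0.446). At a true rate of 0.2 or below the difference is negligible.

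The result rests on the stated prior, a maximum of 40 patients and looks every five patients from the tenth. The tables exclude 0.92 and are consistent with 0.95, but do not prove that 0.95 was the value used. Nothing elsewhere in the document resolves the conflict.

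**What to change.** State one cut-off in section 1.3 and make the formula, explanation and tables agree with it. The sponsor should confirm which was intended.

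- **If 0.95:** replace 0.92 with 0.95 in the formula. The explanation and Tables 3a and 3b already agree, so this is the smallest change.
- **If 0.92:** change the explanation to 92%, and change Table 3a to 13 at n = 30 and 15 at n = 35. Restate the Table 3b early-stop probabilities as 0.0002, 0.012, 0.142, 0.531, 0.887 and 0.991. Change the median sample size at a true rate of 0.4 from 40 to 35; the other printed percentiles do not change.

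In either case, add a sentence saying that toxicity is assessed at the looks listed in Table 3a. The cost is wording only, plus a re-run of Table 3b if 0.92 is kept. Sample size and data collection are unaffected.
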